5.3.3 Device Deficiencies

The number and percentage of all device deficiencies will be tabulated. A listing of all device deficiencies, as recorded on the Device Deficiency Form, will also be provided.

5.3.4 Fundus Visualization

Fundus visibility will be assessed by mydriatic slit lamp examination. Fundus visibility will be judged as no (no difficulty) or yes (difficulty). The results of fundus visibility will be summarized in each category using the number and percentage of eyes by first and second implanted eye at each scheduled visit where the data are collected. Eyes with difficulty in fundus visualization will be summarized and sorted by first or second eye, by subject identification (investigator number, subject number) and by visit. Eyes with missing follow-up values of fundus visualization will be summarized and sorted by first or second eye, by subject identification (investigator number, subject number) and by visit. The listing will include the following variables: investigator, subject, age, sex, visit, eye and no difficulty/difficulty at the visit.

5.3.5 Intraocular Pressure

Intraocular pressure (IOP) measurements will be recorded in mmHg and rounded to the nearest whole mmHg. Descriptive summaries (mean, standard deviation, N, median, minimum and maximum) of observed values and change from baseline values will be presented at each study visit. Eyes with missing follow-up values of intraocular pressure will be summarized and sorted by first or second eye, by subject identification (investigator number, subject number) and by visit. A listing will be provided which presents all eyes with an increase or decrease in IOP of more than 10 mmHg at any visit compared to the same eye at baseline. The listing will include the following variables: investigator, subject, age, sex, visit, eye, baseline value, value at the visit and a change from baseline value.

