#### (4) Eye Examinations Schedule

As shown in Table 6-1, the examination and observation are carried out for the period from before surgery day 120 to 180 after surgery of second eye. At Visit 0 and Visit 4A, the examination and observation of both eyes are carried out on the same day.

Both the examination and the observation may be per Visited on the same day if the day is within the window for the examination and observation of the eye concerned (first or second operated eye). Also examination and observation can be performed separately over days if these are performed within the set window.

Table 6-1 Eye Examinations Schedule

PROCEDURES/ MEASUREMENTS/ STATUS	Visit 0 (Preop)	Visit 00 (Op)	Visit 00A (Op)	Visit 1 (d1-2)	Visit 1A (d1-2)	Visit 2 (d7-14)	Visit 2A (d7-14)	Visit 3 (d30-60)	Visit 3A (d30-60)	Visit 4A (d120-180)
Informed Consent*	X									
Demographics	X									
Inclusion/Exclusion Criteria	X	1 st	2 nd							
Urine Pregnancy Test (female only)	X									
Intraocular Pressure	B			1 st	2 nd	1 st	2 nd	1 st	2 nd	B
Laser Flare Meter (mydriatic)						1 st	2 nd			(1 st ) (2 nd )
Slit Lamp Examination	B			1 st	2 nd	1 st	2 nd	1 st	2 nd	B
Dilated Fundus Examination	B					1 st	2 nd			B
Fundus visualization						1 st	2 nd			B
IOL Observations				1 st	2 nd	1 st	2 nd	1 st	2 nd	B
Lens decentration and tilt				1 st	2 nd	1 st	2 nd	1 st	2 nd	B
Subjective Posterior Capsule Opacification / Posterior Capsulotomy					1 st	2 nd	1 st	2 nd	1 st	2 nd
Subjective Symptoms	X b								X b	X b
Operation Records**			1 st	2 nd						
Ocular Concomitant Medications	B	1 st	2 nd	1 st	2 nd	1 st	2 nd	1 st	2 nd	B
Secondary Surgical Interventions				1 st	2 nd	1 st	2 nd	1 st	2 nd	B
Device Deficiencies	↔									
Adverse Events	↔									

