### 3) Postoperative Examinations

Below examination and observation are carried out at Visit 1/1A, Visit 2/2A, Visit 3/3A and Visit 4A.

- Visual acuity

Visual acuity is tested under photopic [REDACTED] using the 100% contrast chart at each measurement distance as below. [REDACTED]  
[REDACTED]  
[REDACTED]

- **Subjective Symptoms (Visit 3A, Visit 4A: Binocular)**

To the following inquiries by the investigator, the subject will declare the following Subjective symptoms.

- Intraocular Pressure (Visit 1/1A, Visit 2/2A, Visit 3/3A: Monocular (1st or 2nd eye), Visit 4A: Both eyes)

Perform tonometry using a contact or a non-contact ocular tonometer.

- Laser Flare Meter (Visit 2/2A: Monocular (1st or 2nd eye), Visit 4A: Both eyes)

Perform examination using a laser flare meter at mydriatic condition. If there is any inflammation sign at Visit 2 or Visit 2A in laser flare meter and Slit lamp examination, perform examination again at Visit 4A.

- Slit Lamp Examination (non-mydriatic or mydriatic)

(Visit 1/1A, Visit 2/2A, Visit 3/3A: Monocular (1st or 2nd eye), Visit 4A: Both eyes)

Record the presence or absence of clinically significant ophthalmologic findings.

- Dilated Fundus Examination (Visit 2/2A: Monocular (1st or 2nd eye), Visit 4A: Both eyes)

Record the presence or absence of clinically significant ophthalmologic findings.

- Fundus visualization (Visit 2/2A: Monocular (1st or 2nd eye), Visit 4A: Both eyes)

Indicate whether the investigational lens has caused any loss in fundus visualization that would alter a surgeon's ability to administer retinal treatment, as compared to experience with monofocal IOLs.

- IOL observation (Visit 1/1A, Visit 2/2A, Visit 3/3A: Monocular (1st or 2nd eye), Visit 4A: Both eyes)

[figure not shown]
Observe the IOL surface and the inside of the haptic and optic of the investigational lens with a slit-lamp microscope, and record the presence/absence of visible abnormal findings (debris on IOL surface, forceps mark on IOL surface, glistening, formation of membrane on IOL, pigmentation on IOL, etc.). And regarding the observed findings, evaluate the clinical significance. If the problem may negatively affect postoperative visual acuity, etc., handle it as the clinical significant, and if possible, take photos.

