## 9.6 Safety Analysis

Patient listings will be provided for adverse experiences occurred from informed consent to exposure to the test article using Pre-Treatment Safety Analysis Set. Safety variables below will be analyzed using Treatment-Emergent Safety Analysis Set. For continuous variables, descriptive statistics (mean, standard deviation, N, median, min and max) will be provided for actual value and change from baseline at each visit. For categorical variables, N and percent will be provided for each category at each visit.

- Secondary Surgical Interventions related to the optical properties of the IOL
- Adverse Events (including secondary surgical interventions not-related to the optical properties of the IOL)
- Device Deficiencies
- Fundus visualization
- Intraocular Pressure
- Slit Lamp Examination
- Dilated Fundus Examination
- IOL Observations
- Subjective Posterior Capsule Opacification
- Posterior Capsulotomy
- Lens decentration and tilt
- [REDACTED]
- Laser Flare meter

- Subjective symptoms
- Problems during surgery

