## APPENDIX B: Definition of Adverse Events

Following findings are not regarded as AE because that it is a series of wound healing reaction related to cataract surgery. However, when investigator judged it is not wound healing reaction, it is treated as AE.

- Edema or haze around sclerocorneal incision: Occurred by 1 month post surgery
- Fold or swelling of Descemet's membrane at central cornea: Occurred by 1 month post surgery
- Post surgery inflammation: Occurred by 3 months post surgery
- Raised IOP related to post operation inflammation and fibrin reaction: Occurred by 1 month post surgery

Investigator (or sub-investigator) should judge when the events below occurred after the test IOL implantation whether the events is AE or not.

If the events are regarded as AE, investigator must fill out AE forms in the electric case report forms.

- IOP: 10mmHg or more than 10 mmHg change from Visit 0 after 1 month post surgery
- Slit lamp findings (anterior and posterior segment): Worse than Visit 0  
(Ocular finding which is caused by inflammation related to cataract surgery is excluded.)
- Best corrected distance visual acuity: Worse than Visit 0 at the last exam (Visit 4A)

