5.3 Statistical Methods for Safety Analyses

Except otherwise stated, the analysis set for all safety analyses is the safety analysis set as defined in Section 2.2. Baseline will be defined as the last measurement prior to exposure to investigational product, except otherwise stated.

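### Should the SAP's intraocular pressure listing start at a change of exactly 10 mmHg, to match the review prompt in protocol Appendix B?

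*SAP*

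**What the plan says.** SAP section 5.3.5 plans three visible IOP outputs: visit-by-visit summaries of values and changes, a listing of eyes with missing follow-up readings, and a listing by size of change. On the last it says: "A listing will be provided which presents all eyes with an increase or decrease in IOP of more than 10 mmHg at any visit". The comparison is with the same eye at baseline. Readings "will be recorded in mmHg and rounded to the nearest whole mmHg".

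SAP section 5.3 sets the reference value: "Baseline will be defined as the last measurement prior to exposure to investigational product, except otherwise stated".

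Protocol Appendix B has a separate rule. Among the findings on which the investigator "should judge when the events below occurred after the test IOL implantation whether the events is AE or not" is "IOP: 10mmHg or more than 10 mmHg change from Visit 0 after 1 month post surgery". An AE form follows only if the answer is yes.

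For continuous safety variables, protocol section 9.6 asks that "descriptive statistics (mean, standard deviation, N, median, min and max) will be provided for actual value and change from baseline at each visit". It does not ask for an IOP listing.

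**The concern.** Both rules concern the same measurement, use the number 10, and normally take the same preoperative reading as reference. One includes 10 and the other excludes it, and no reason is given. The listing covers every visit, so a reader would expect it to contain every eye that the protocol prompts the investigator to consider. With whole-number readings, 10 is an ordinary value, so the difference between the two wordings is not merely theoretical.

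What is at stake is visibility. An eye judged to have an AE is shown in the AE listings. An eye at exactly 10 that is judged not to have one is identified for its pressure change nowhere in the visible SAP. In a single-arm, open-label study, a later reader who wanted to look again at that judgement could not find the eye from the planned outputs.

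**Working it through.** The plan gives no IOP mean change, SD or expected count, so there is no planned figure to reproduce. The check has four parts.

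**1. Compare the two rules.** Let d be the whole-mmHg change from the preoperative reading.

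- Appendix B prompt: |d| ≥ 10, after one month.
- SAP listing: |d| > 10, which for whole numbers is |d| ≥ 11, at any visit.
- Values that meet the prompt's size limit but not the listing's: −10 and +10.
- Values that meet the listing's size limit but not the prompt's: none.

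| Largest \|d\| over all visits | Timing | Prompted | Listed |
|---|---|---|---|
| 9 or less | any | no | no |
| 10 | reached only in the first month | no | no |
| 10 | reached after one month | yes | **no** |
| 11 or more | below 10 after one month | no | yes |
| 11 or more | 10 or more after one month | yes | yes |

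Only the third row is a gap. The fourth shows that the listing is wider than the prompt in time.

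**2. How exact is a recorded 10?** Each reading is rounded before subtraction, with an error of up to 0.5 mmHg. A recorded change of 10 can therefore stand for an unrounded change between 9 and 11. For example, 14.4 to 24.6 is a true change of 10.2 but is recorded as 25 − 14 = 11. A move from 14.6 to 24.4 is a true change of 9.8 but is recorded as 24 − 15 = 9.

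**3. Is the reference value the same?** Normally, yes. In protocol Table 6-1, Visit 0 is the only scheduled preoperative IOP, and "At Visit 0 and Visit 4A, the examination and observation of both eyes are carried out on the same day". After surgery the schedule is "Intraocular Pressure (Visit 1/1A, Visit 2/2A, Visit 3/3A: Monocular", so no second-eye reading is scheduled between Visit 0 and that eye's own surgery. However, the second operation may follow the first by up to 30 days, and unscheduled examinations are allowed. A later pre-exposure reading in the second eye would become its SAP baseline and would not be Visit 0. Equal cut-offs would therefore not guarantee that every prompted eye is listed.

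**4. Possible size, on assumed inputs.** Take d as a rounded Normal(μ, σ). At one visit,

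P(d = ±10) = [Φ((−9.5−μ)/σ) − Φ((−10.5−μ)/σ)] + [Φ((10.5−μ)/σ) − Φ((9.5−μ)/σ)].

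With μ = −1.5 and σ = 4:

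[Φ(−2.00) − Φ(−2.25)] + [Φ(3.00) − Φ(2.75)] = 0.0105 + 0.0016 ≈ 0.0122.

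Times 120 eyes, this is 1.46 per visit. About 87% of these are falls in pressure (0.0105 of 0.0122). With μ = 0 and σ = 2.5 the figure is 0.01; with μ = −2 and σ = 5 it is 3.21.

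Per eye, four postoperative visits with equal correlation were simulated (2,000,000 eyes per scenario). An eye is prompted if |d| ≥ 10 at either of the last two visits. It is not listed if its largest |d| over all four visits is 10.

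| μ | σ | Correlation | Prompted per 120 | Of these, not listed |
|---|---|---|---|---|
| 0 | 2.5 | 0.7 | 0.03 | 0.02 |
| −2 | 2.5 | 0.3 | 0.32 | 0.23 |
| −1.5 | 4 | 0.5 | 5.66 | 2.30 |
| −2 | 5 | 0.3 | 17.15 | 4.84 |
| −2 | 6 | 0.3 | 28.65 | 5.85 |

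The Visit 3 window opens at day 30, so it is arguable whether Visit 3 counts as after one month. If only Visit 4A counts, the middle row becomes 1.17 of 3.07. All counts include eyes judged to have an AE, which are shown elsewhere. Within each scenario they therefore overstate the gap by an unknown share.

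**The case for a change.** The case for a change is that it is almost free: one phrase and one listing filter. At SDs of 2.5 to 5 it would add roughly 0.01 to 3.2 eye records per visit. Appendix B spells out that 10 itself counts, so its boundary does not look like loose wording. A by-eye listing also adds most for the eyes judged not to have an AE, because the others are displayed already.

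Much of this stands. The texts differ, the boundary is reachable, and the cost is small. What does not follow is that the plan is deficient. The listing already goes beyond what protocol section 9.6 asks. Nothing visible shows that SAP listings are meant to mirror Appendix B: its trigger for worse corrected distance acuity at Visit 4A has no matching listing in the visible SAP either. The documents do not say whether the strict cut-off was deliberate, so choosing one boundary over the other would be a preference.

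The eye in question is not lost. The investigator has considered that very change, and protocol section 10(3) separately calls for AE reporting of changes judged clinically relevant. The reading also enters the visit mean, SD, median, minimum and maximum.

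**Conclusion.** No change to the plan follows. The mismatch is a small editorial inconsistency between a prompt for clinical judgement and a display filter, limited to changes of exactly +10 or −10 mmHg. It affects only eyes that peak at that value, after one month, and are judged not to have an AE. Aligning the cut-offs would move no primary result, AE count or conclusion, and would not ensure complete overlap because the two reference readings can differ in the second eye.

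The number of eyes concerned cannot be derived from the documents. The assumed scenarios run from 0.02 to 5.9 of 120 before removing those judged to be AEs, which says little more than possibly none, possibly a few. They rest on normally distributed changes, equal correlation between visits, and complete data on all 120 eyes. The statement that no other output identifies such an eye covers the visible SAP only, since parts are redacted.

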5.3.6 Slit Lamp Examination

For each slit-lamp parameter, number and percentage of each category will be provided by visit. Also, number and percentages of eyes that experience abnormality at any post-operative visit will be presented. Eyes with missing follow-up values of slit-lamp examination will be summarized and sorted by first or second eye, by subject identification (investigator number, subject number) and by visit. A listing will be provided which presents all eyes with an abnormality in any slit-lamp parameter at any post-operative visit. The listing will include all slit-lamp data from all visits with the following variables: investigator, subject, age, sex, visit, eye and normal/abnormal findings at the visit.

5.3.7 Dilated Fundus Examination

For each dilated fundus parameter, number and percentage of each category will be provided by visit. Also, number and percentages of eyes that experience abnormality at any post-operative visit will be presented. Eyes with missing follow-up values of dilated fundus examination will be summarized and sorted by first or second eye, by subject identification (investigator number, subject number) and by visit. A listing will be provided which presents all eyes with abnormality in any fundus parameter at any post-operative visit. The listing will include the following variables: investigator, subject, age, sex, visit, eye and normal/abnormal findings at the visit.

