#### (3) Exclusion Criteria

[Exclusion Criteria Prior to Surgery]

The patient who meets any criteria specified in the following 1) through 21).

- 1) Significant irregular corneal aberration as demonstrated by corneal topography;
- 2) Inflammation or edema (swelling) of the cornea affecting post-operative visual acuity;
- 3) Subjects with diagnosed degenerative visual disorders (e.g. macular degeneration or other retinal disorders) that are predicted to cause future acuity losses to a level worse than 0.5 decimal for BCDVA;

- 4) Subjects who may be expected to require ocular surgery (other than blepharo-surgery, laser surgery of fundus and YAG capsulotomy) during the study;
- 5) Previous refractive surgery;
- 6) Amblyopia;
- 7) Clinically severe corneal dystrophy (eg., epithelial, stromal, or endothelial dystrophy), keratitis, keratoconjunctivitis, keratouveitis, keratopathy, or kerectasia;
- 8) Diabetic retinopathy;
- 9) Extremely shallow anterior chamber, not due to swollen cataract;
- 10) Microphthalmos;
- 11) Previous retinal detachment;
- 12) Previous corneal transplant;
- 13) Recurrent severe anterior or posterior segment inflammation of unknown etiology;
- 14) Rubella or traumatic cataract;
- 15) Iris neovascularization;
- 16) Glaucoma;
- 17) Aniridia;
- 18) Optic nerve atrophy;
- 19) Pregnancy;
- 20) Any subject currently participating in another investigational drug or device study.
- 21) Disqualified by the investigator or the sub-investigator because of physical or ophthalmic diseases

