### 1) Preoperative Examination (Visit 0)

- Informed consent

Routine test conducted for cataract subjects is performed. Subjects still qualifies after these tests are explained this study. Ensure that the subject has read, understood, and signed and dated a statement of informed consent prior to undergoing any study specific testing. Even though routine test was operated before informed consent, these data can be use as study data.

- Demography

Sex, age, systemic complication, ophthalmologic surgical history

- Urine Pregnancy Test (female subjects only)

Perform a urine pregnancy test if the subject is female and of childbearing potential.

- Visual acuity

Measure the monocular visual acuity about both eyes. Measure the visual acuity [REDACTED]

[REDACTED] using the 100% contrast chart at each measurement distance as below.

[REDACTED]

[figure not shown]
[REDACTED]

[REDACTED]

[REDACTED]

- Subjective Symptoms

[figure not shown]
To the following inquiries by the investigator or co-investigator, the subject will declare the following Subjective symptoms.

- Target Residual Refractive Error

Indicate the amount of postoperative refractive error ( $\pm$ ) anticipated based on the power calculation software used for the lens power that is chosen. [REDACTED]

- Intraocular pressure

Perform tonometry using a contact or a non-contact ocular tonometer.

- Slit Lamp Examination

Record the presence or absence of clinically significant ophthalmologic findings.

- Dilated Fundus Examination

Record the presence or absence of clinically significant ophthalmologic findings.

- Ocular concomitant medications

Indicate the type of concomitant ocular medications used by the subject at the time of the examination.

- Inclusion/exclusion criteria

Ensure that the subject meets inclusion/exclusion criteria and meet all qualifications for participation.

- Adverse Events, Device Deficiencies

Presence/absence of adverse events and device deficiencies are recorded since informed consent.

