## (3) Report of adverse events and evaluation of the causal relationship

All adverse events (related and unrelated to the medical device or test procedures) will be entered in the Adverse Event form. Surgically-related post-operative conditions that are normal consequences of the ocular surgery (see Appendix B) and not clinically relevant will be only reported as adverse events at the discretion of the investigator.

In addition, the investigator must document all serious adverse events (related and unrelated) on the Serious Adverse Event Form. Any device deficiencies will be entered in the device deficiency form within 24 hours

[figure not shown]
after confirming the event.

Adverse events will also be reported for any clinically relevant change from screening in any protocol specific safety parameter evaluated during the study, based upon an assessment by the investigator following exposure to an investigational product.

Regarding the relationship with the investigational lens, a judgment will be made whether “not related” or “related.” Adverse events will be reported for any change in an ongoing medication and/or addition of a new medication, based upon an assessment by the investigator.

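### The cumulative slit-lamp and dilated-fundus rows in SAP 5.3.6 and 5.3.7 count findings already present at Visit 0 and cannot separate them from findings new after implantation

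*SAP*

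**What the plan says.** SAP 5.3.7 tabulates each fundus parameter by visit and then adds a cumulative row: "number and percentages of eyes that experience abnormality at any post-operative visit will be presented". SAP 5.3.6 does the same for the slit lamp: "Also, number and percentages of eyes that experience abnormality at any post-operative visit will be presented". Neither row has a condition on the preoperative result, and neither section plans a shift table or a count of new findings.

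The preoperative result is available. Protocol Table 6-1 schedules both examinations in both eyes at Visit 0, and Protocol 6(5) gives the instruction "Record the presence or absence of clinically significant ophthalmologic findings". The postoperative instruction is the same. SAP 5.3 also supplies a reference point, "Baseline will be defined as the last measurement prior to exposure to investigational product, except otherwise stated", but 5.3.6 and 5.3.7 do not use it.

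The two listings differ. For eyes with a postoperative slit-lamp abnormality, "The listing will include all slit-lamp data from all visits". The fundus listing has no such sentence. It names the visit and the finding at that visit, and does not say whether Visit 0 is shown.

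Elsewhere the protocol refers to change. Appendix B asks the investigator to judge as a possible adverse event "Slit lamp findings (anterior and posterior segment): Worse than Visit 0", and section 10(3) calls for adverse event reporting of "any clinically relevant change from screening in any protocol specific safety parameter".

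**The concern.** Some eyes can enter the study with a lasting abnormality. Retinal disorders are excluded only if they are of a kind "that are predicted to cause future acuity losses to a level worse than 0.5 decimal for BCDVA", and corneal dystrophy and related disease only if clinically severe. The macular degeneration filter applies to the Best-Case Analysis Set, not to the safety set, which takes every eye with attempted implantation whatever was seen at Visit 0.

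With no control arm, each eye's own preoperative result is the only internal reference for telling background disease from something that arose after surgery. A cumulative row that ignores it answers a different question from the one a safety reader will ask. The reader sees how many eyes were abnormal at some point after surgery, but not how many became abnormal. Describing safety is a stated purpose of the study, so the descriptive rates are its product.

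**Working it through.** **The plan's own figures.** The documents give no expected value for the slit-lamp or fundus rates, so there is none to reproduce. The only stated precision figures (SAP 8) do reproduce: t(0.975, 59)/√60 = 2.001/7.746 = 0.258, which rounds to 0.26 SD, and the exact interval for 30/60 is 36.8% to 63.2%.

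**Which visit is the baseline.** In Table 6-1, the only scheduled slit-lamp or fundus examination of either eye before its own surgery is Visit 0. For both eyes the SAP 5.3 baseline is therefore Visit 0, unless an unscheduled examination intervenes.

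**What the row measures.** Let b be the share of eyes abnormal at Visit 0, s the share of those still abnormal after surgery, and q the risk of a new abnormality. None of the three is in the documents; all are assumptions. The row then shows

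R = b[s + (1 − s)q] + (1 − b)q,

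and its excess over the new-onset risk is R − q = b·s·(1 − q).

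With b = 10%, s = 1, q = 2%: R = 0.10 + 0.90 × 0.02 = 0.118, an excess of 0.10 × 0.98 = 0.098.

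Values of R at q = 2%:

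| b | R if s = 1 | R if s = 0.5 |
|---|---|---|
| 0 | 2.0% | 2.0% |
| 5% | 6.9% | 4.45% |
| 10% | 11.8% | 6.9% |
| 20% | 21.6% | 11.8% |

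If b = 0 or s = 0, the row equals the new-onset rate.

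**Why the row cannot be unpicked.** Suppose it shows 6 of 60 first eyes, 10% (exact 95% CI 3.8% to 20.5%). All 6 may be new. Equally, all 6 may have been abnormal at Visit 0, in which case the new-onset result is 0 of 54 (upper 95% limit 6.6%). The row is the same in both cases.

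**Whether other planned output separates them.**
- By-visit tables: if Visit 0 is included, they give marginal counts. Six abnormal eyes at Visit 0 and six at Visit 4A need not be the same eyes.
- Slit-lamp listing: shows all visits, so a reader can trace each eye by hand.
- Fundus listing: does not state that Visit 0 is included.
- Adverse event tables (SAP 5.3.2): these use a comparison with Visit 0 or screening, but only for changes judged to be adverse events. Appendix B also sets aside slit-lamp findings caused by surgical inflammation.

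**The case against.** The strongest reply is that new or worsened findings that matter clinically already have a per-eye rate. Protocol 10(3) and Appendix B direct them to the adverse event form, and SAP 5.3.2 tabulates eyes with ocular adverse events. This stands as far as it goes. A reader might infer that the cumulative rows are the study's only incidence figure for these endpoints, and the documents do not support that. What remains is that the adverse event route depends on investigator judgement and is not a rate taken from the examinations.

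Second, the SAP does not label the row as incidence or attribute it to the lens. This is correct: the row is a valid period-prevalence count, not a wrong figure.

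Third, a reader might see an inconsistency with intraocular pressure, which SAP 5.3.5 compares with baseline. There is none. Protocol 9.6 plans change from baseline for continuous variables, and counts and percentages per visit for categorical ones.

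Fourth, a reader might take 11.8/2 = 5.9 as an estimate of the overstatement. The ratio is produced by the chosen inputs. With q = 5% and the same b and s, R is 14.5% and the ratio is 2.9; with b = 0 it is 1. Several features limit b: the exclusion of diabetic retinopathy, glaucoma, optic nerve atrophy and previous retinal detachment, the requirement for clear media apart from cataract, and the recording of clinically significant findings only. Nor does the Best-Case set's macular degeneration rule show that affected eyes are expected, since it also covers onset after surgery.

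Finally, nothing is tested and no success criterion exists, so no decision rule changes. The row also cannot fall below the number of eyes with a new finding. Both points are true and limit the weight of the concern.

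**Conclusion.** The concern holds in a limited form. As worded, the cumulative rows in SAP 5.3.6 and 5.3.7 include eyes whose abnormality was already present at Visit 0, and no within-eye comparison with Visit 0 is planned for either examination. The gap is wider for the fundus, because its listing does not commit to showing Visit 0. The excess over the new-onset rate is b·s·(1 − q). It is zero if no Visit 0 finding persists, and 9.8 percentage points in the illustration with b = 10%, s = 1 and q = 2%. Because b, s and q are assumed, no size can be claimed for this trial. This is an inexpensive improvement to a reported safety result, not the correction of an erroneous figure.

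**What to change.** In SAP 5.3.6 and 5.3.7, keep the existing row and split it, per parameter and within the same eye, into:

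- (a) eyes without the abnormality at Visit 0 that show it at one or more visits after surgery, with eyes free of that abnormality at Visit 0 as the denominator; and
- (b) eyes in which the abnormality was already present at Visit 0.

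The split should be per parameter. If cataract is itself recorded as a slit-lamp finding at Visit 0, a single eye-level flag would class every eye as abnormal before surgery.

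State in 5.3.7 that the fundus listing shows the Visit 0 result, as the slit-lamp listing already does.

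Do not ask for a flag for findings less severe at Visit 0. The documents describe presence or absence and normal or abnormal for these examinations, with no severity grade, so worsening cannot be derived from the data described.

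The cost is a short SAP wording change, one derived flag per parameter, the extra table rows and, if Visit 0 is not already shown, its result in the fundus listing. No new assessment or data collection is needed.
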